5.2. Participant Dispositions

Screened participants and reason for screen failures will be summarized overall.

The number of participants in the following disposition categories will be summarized throughout the study by intervention group and overall:

- Participants randomized
- Participants who received study intervention
- Participants who completed the study
- Participants who discontinued study intervention
- Reasons for discontinuation of study intervention
- Participants who terminated study prematurely
- Reasons for termination of study

A listing of participants will be provided for the following categories:

- Participants who discontinued study intervention
- Participants who terminated study prematurely
- Participants who were unblinded during the study period
- Participants who were randomized yet did not receive study intervention.

5.3. Primary Endpoint(s) Analysis

PVR data will be listed only.

5.3.1. Definition of Endpoint(s)

The primary endpoint is the ratio of the PVR value post-treatment initiation up to Week 26 (post) vs the PVR value pre-treatment initiation at baseline (pre), expressed as a percentage, ie:

$$PVR \text{ post to pre percent} = \left(\frac{PVR \text{ up to Week 26}}{PVR \text{ at baseline}} \right) \times 100 (\%)$$

The baseline reference value for PVR is based on the last RHC performed prior to study intervention initiation.

At each assessment, PVR (dyn.sec/cm⁵) is derived as follows:

$$PVR = 80 \times (mPAP - PAWP) / CO$$

where mPAP is mean pulmonary artery pressure measured in mmHg, PAWP is pulmonary artery wedge pressure measured in mmHg, and CO is cardiac output measured in L/min. If PAWP is missing, then the LVEDP will be used.

Handling of missing data

No imputation will be performed for missing PVR.

5.3.2. Analysis Methods

PVR data will be listed only using the Randomized Set (RS).

5.4. Secondary Endpoint(s) Analysis

Not applicable. For efficacy, the study has only primary and exploratory endpoints.

5.5. Tertiary/Exploratory Endpoint(s) Analysis

All exploratory endpoints will be listed only using the Randomized Set (RS).

5.5.1. Time To Clinical Worsening (TTCW)

No event adjudication will be performed by the Clinical Event Committee (CEC). Therefore, no data will be reported for this endpoint.

5.5.2. 6-Minute Walk Distance (6MWD) and Borg CR Scale® (CR10)

6MWD and Borg Scale will be listed only using the Randomized Set (RS).

5.5.3. Proportion of participants with oxygen desaturation post 6MWT up to Week 39

Oxygen desaturation will be listed only using the Randomized Set (RS).

5.5.4. Proportion of participants with improvement/no change/worsening versus baseline in WHO FC up to Week 39

WHO FC will be listed only using the Randomized Set (RS).

5.5.5. Daily life physical activity (DLPA) and sleep parameters up to Week 39

Actigraph data as per source transfer as documented in the data transfer agreement (instead of derived data) may be reported in listings (on the Randomized Set (RS) as we may not have sufficient data for derivation.

If derived, the following variables will be computed and listed over time on the Randomized Set (RS):

- Total DLPA in counts per minute
- Total volume of activity (above sedentary)
- Daily time spent (minutes) in non-sedentary activity
- Percentage of daily time spent in non-sedentary activity
- Moderate to vigorous physical activity (MVPA)
- Time spent in the different activity categories

All actigraphy endpoints will be aggregated into 14-day windows for analysis. Baseline will be the average of the last 14 days prior to first dose of study drug (Day -1 to Day -14); post baseline assessments will be aggregated in 14-day intervals as shown in [Table 5](#).

Likewise, the last 14 days prior to the last dose of study treatment will be used for determination of the EOT value. All patients will have an EOT value, unless patient withdrew within a week of treatment start or no actigraphy data available after the study day 7 (See section "Handling of missing data").

If enough valid data have been collected in a time window at an analysis visit (see Section Handling of missing data"), the average of the values assessed within the time window will be used as analysis value. Actigraphy data collected prior to Day -14 or after EOT will be listed only.

Table 5 Actigraphy assessment time windows

Analysis Visit	Start Day	End Day
Baseline	-14	-1
Week 3	8	21
Week 5	22	35
Week 7	36	49
Week 9	50	63
Week 11	64	77
Week 13	78	91
Week 15	92	105
Week 17	106	119
Week 19	120	133
Week 21	134	147
Week 23	148	161
Week 25	162	175
Week 27	176	189
Week 29	190	203
Week 31	204	217
Week 33	218	231
Week 35	232	245
Week 37	246	259
Week 39	260	273
EOT ¹	Last study treatment - 14 days*	Last study treatment - 1 day*

¹ EOT value will be computed out of the last two weeks prior to last study treatment, regardless if the last study treatment date was before, at, or after Day 273.

* EOT will have a valid value. If EOT value based on the period (EOT-14, EOT-1) is missing (not valid), the EOT period will be rolled back by one day, i.e., (EOT-15, EOT-2), (EOT-16, EOT-3), and so on until a non-missing (valid) value is available. The period can be rolled back until (1, 14).

EOT = End-of-Treatment.

Handling of missing data

Actigraphy variables will be considered valid (non-missing) for a specific time window if the data are available for at least 7 complete days (consecutive or not) within that time window of assessment.

For DLPA actigraphy endpoints, a complete day is defined as a record of at least 7 awake hours of data. If less than 7 complete days are available, the value of the time window will be set to missing.

In case of premature discontinuation of study drug, the average of the last non-missing 14-day window prior to the last dose of study treatment will always be used as an EOT value. If the EOT value corresponding to the period (EOT-14, EOT-1) is missing (not valid), the EOT period will be rolled back by one day, i.e., (EOT-15, EOT-2), (EOT-16, EOT-3), until a non-missing (valid) value is available. This corresponds to a last observation carried forward (LOCF) up to Week 39/EOT approach. If no post-baseline actigraphy data have been collected for at least 7 days over a 14-day time window, no EOT value will be computed, and the post-baseline value will be set as missing.

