  - g. Assessment not collected in eCRF.
  - h. In case of twice daily dosing, first dose to be taken in the evening of Day 1. In case of once daily dosing, the first dose of study intervention should be taken in the morning of Day 2. Includes study intervention up-titration (see Section 6.1.3 for detailed information).
  - i. A historical RHC is allowed taking into account the restrictions provided in Section 8.2.1.1.1. If no historical results are available, an RHC must be performed during the Screening period only if all other inclusion criteria are met and none of the exclusion criteria is met.
  - j. If the 6MWT and RHC are assessed on the same day the RHC should be performed after the 6MWT and within 2 to 5 hours post-dose.
  - k. To be performed within 2 to 5 hours post-dose and prior to the RHC (if applicable).
  - l. To collect baseline data, participants should wear the actigraphy device 14 days between Visit 1 (Screening) and Visit 2 (Randomization). It is recommended to start on the day following the screening visit. If required, the baseline RHC should not be done during this time.
  - m. To assess baseline, the PAH-SYMPACT™ questionnaire should be completed on 7 consecutive days starting on the day following the screening visit. If required, the baseline RHC should not be done during the 7 consecutive days of the PAH-SYMPACT completion.
  - n. If the results for the screening blood samples from the central laboratory are not available in time for randomization of the participant, an additional blood sample may be drawn to verify eligibility based on a local laboratory test.
  - o. A historical ABG is allowed taking into account the restrictions provided in Section 8.3.6. If no historical results are available, an ABG must be performed during the Screening period.
  - p. The ABG can be done during the RHC taking into account the restrictions provided in Section 8.3.6.
  - q. All AE and SAEs will be reported throughout the study from signing of the ICF onwards until the EOS visit (see Section 4.4.1) or death or lost to follow-up (see Section 7.3).
  - r. Optional assessment.

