| 
 
To evaluate the effect of selexipag vs placebo on daily life physical activity (DLPA) and sleep parameters.
 
 | 
 
Change from baseline to Week 39 in actigraphy-assessed DLPA as measured by: 
 
Total DLPA in counts per minute
 
Total volume of activity (above sedentary)
 
Daily time spent (minutes) in non-sedentary activity
 
Percentage of daily time spent in non-sedentary activity
 
Moderate to vigorous physical activity (MVPA)
 
Time spent in the different activity categories
 
 
 
Change from baseline to Week 39 in sleep parameters: 
 
Total sleep time (TST; minutes)
 
Wake after sleep onset (WASO; minutes)
 
Number of awakenings
 
Sleep efficiency (percentage)
 
 
 
 |
| 
 
To evaluate the effect of selexipag versus placebo on WHO FC.
 
   | 
 
Proportion of participants with improvement, worsening and no change from baseline in WHO FC at Week 39 and over time.
 
   |
| 
 
To evaluate the effect of selexipag versus placebo on death or PH-related hospitalizations.
 
                 | 
 
Rate of all-cause death or unplanned PH-related hospitalization up to EOMOP.
 
Time to all-cause death up to EOMOP.
 
   |

| Objectives   | Endpoints  |
|--|--|
| 
 
To evaluate the effect of selexipag versus placebo on patient-reported outcomes (PROs) assessed by the 12-Item Short Form Health Survey (SF-12), King's sarcoidosis questionnaire (KSQ), Pulmonary Arterial Hypertension-Symptoms and Impact (PAH-SYMPACT), and Patient Global Assessment of Severity (PGA-S).
 
 | 
 
Change from baseline up to Week 39 in SF-12 scores.
 
Change from baseline up to Week 39 in KSQ scores.
 
Change from baseline up to Week 39 in PAH-SYMPACT scores.
 
Change from baseline up to Week 39 in PGA-S scores.
 
 |

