#### **8.2.2.3.2. Daily Life Physical Activity (DLPA) and Sleep Parameters**

DLPA and sleep parameters are assessed via an actigraphy device. The device is given to the participant at Visit 1 (Screening Visit), and the participant is instructed to wear the actigraphy device on the wrist for 2 weeks during the screening period and following site visits. Detailed instructions for use of the actigraphy device and accessories are provided to participants via a participant guide.

The actigraphy device does not display collected data, ie, the participants do not have access to their activity measurements, as this could influence their behavior. Data will be uploaded to the vendor as described in the participant guide.

The data received will be monitored for compliance. Should corrective actions be necessary, participants may be contacted from the site staff.

The data from the actigraphy device will be collected by the vendor, who will send the results to the sponsor, but the results will not be recorded in the eCRF.

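### The SAP's Week 39 actigraphy window (Day 260 to 273) closes before most of the wear that follows the Week 39 visit, so a derived Week 39 activity value would be missing for almost every allowed visit day; minor, because the endpoint is exploratory and listed only

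*SAP*

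**What the plan says.** **Endpoint.** Protocol Section 3 lists, among the exploratory endpoints, "Change from baseline to Week 39 in actigraphy-assessed DLPA as measured by" a set of daily life physical activity (DLPA) variables.

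**Wear.** Protocol 8.2.2.3.2 instructs participants to "wear the actigraphy device on the wrist for 2 weeks during the screening period and following site visits". It does not say on which day post-baseline wear starts, and it leaves detailed instructions to a participant guide. The Schedule of Activities (1.3.1) puts the Week 39 visit at Day 274 ±7 and the preceding site visit, Week 26, at Day 183 ±7.

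**Analysis windows.** SAP 5.5.5 states "All actigraphy endpoints will be aggregated into 14-day windows for analysis", and adds that "post baseline assessments will be aggregated in 14-day intervals as shown in" Table 5. The blocks in that table run back to back from Day 8. The last scheduled row reads "Week 39 260 273", that is, Day 260 to Day 273.

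**Validity.** "Actigraphy variables will be considered valid (non-missing) for a specific time window if the data are available for at least 7 complete days" (SAP 5.5.5). With fewer complete days, the window value is set to missing.

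**Status.** SAP 3.0 was written after early termination. It lists all exploratory endpoints without analysis, and 5.5.5 makes derivation of the DLPA variables conditional.

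**The concern.** The protocol describes separate spells of wear that follow visits. Table 5 divides the calendar as if wear were continuous, and it stops the day before the target Week 39 visit. A participant seen on time who wears the device as the protocol says would contribute nothing to the row that carries the endpoint's stated timepoint.

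If the variables are derived under SAP 5.5.5, a reader of the listing would see Week 39 blank and could take it for non-wear, when the cause is the position of the window. Values from the earlier visits could also appear under week labels that match no site visit.

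**Working it through.** **Inputs**

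- Week 12, 20, 26 and 39 visits: Day 85, 141, 183 and 274, each ±7 (protocol 1.3.1). The Week 39 visit may therefore fall on any of 15 days, Day 267 to 281.
- Wear: 14 days after the visit (protocol 8.2.2.3.2). The start day is an assumption, so both visit day + 1 (next-day) and the visit day itself (same-day) are checked.
- Validity: at least 7 complete days in the window (SAP 5.5.5). All worn days are taken as complete, which favours the plan.

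**Reproducing Table 5.** Each post-baseline row follows Week k = Day 7k − 13 to Day 7k for odd k from 3 to 39. This gives Day 8 to 21 for k = 3, Day 176 to 189 for k = 27 and Day 260 to 273 for k = 39, as printed: 19 contiguous blocks.

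**Overlap formula.** Days in window = max(0, min(wear end, window end) − max(wear start, window start) + 1).

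**Week 39 row.** For a visit on day v, from 267 to 281:

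- Next-day start: wear is v + 1 to v + 14, so the overlap is max(0, 273 − v).
- Same-day start: wear is v to v + 13, so the overlap is max(0, 274 − v).

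| Visit day | Next-day start | Same-day start |
|---|---|---|
| 267 | 6 | 7 |
| 268 | 5 | 6 |
| 270 | 3 | 4 |
| 273 | 0 | 1 |
| 274 to 281 | 0 | 0 |

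Visit days that reach 7: 0 of 15 with next-day start, and 1 of 15 with same-day start (Day 267, and only if the visit day itself counts as complete).

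**Earlier wear cannot fill the row.** The latest allowed Week 26 visit is Day 183 + 7 = 190. Its wear ends by Day 190 + 14 = 204, which is 56 days before Day 260.

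**Where on-time Week 39 wear goes.** Day 275 to 288 (or 274 to 287) lies beyond the last scheduled block.

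**Other on-time visits**

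| Visit | Blocks touched | Next-day split | Same-day split |
|---|---|---|---|
| Day 85 (Week 12) | Week 13 (78–91), Week 15 (92–105) | 6 / 8 | 7 / 7 |
| Day 141 (Week 20) | Week 21 (134–147), Week 23 (148–161) | 6 / 8 | 7 / 7 |
| Day 183 (Week 26) | Week 27 (176–189), Week 29 (190–203) | 6 / 8 | 7 / 7 |

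With next-day start, the block holding the visit fails and the next one passes. With same-day start, both can pass on exactly 7 days.

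**The EOT row.** It takes the 14 days before last dose and rolls back one day at a time until a valid period is found. With on-time visits and next-day wear up to Week 39 only, a last dose on Day 274 rolls back to Day 191 to 204, of which 7 days (191 to 197) are Week 26 wear. Week 39 wear is first reached with a last dose on Day 282 (Day 268 to 281, 7 days: 275 to 281).

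**The case against.** The strongest reply is about weight. SAP 3.0 plans no summary, comparison or test of actigraphy; source data may be listed instead of derived values; and SAP 5.5.16 notes how few participants there are. At most, a row in an optional listing is blank or mislabelled. That stands, and it makes the point minor.

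The second reply is that the wear schedule is loosely worded. No post-baseline start day is given, the participant guide is not available, and the actigraphy row of the schedule is too garbled in the text at hand to confirm which visits are marked. Back-to-back blocks would suit continuous wear. They would also suit wear before the visit: 14 days ending the day before the visit gives a valid Day 260 to 273 value on all 15 visit days. This stands to the extent that the documents need reconciling and Table 5 is not shown to be the only error. It does not remove the mismatch. Continuous wear would leave the 2-week limit without meaning, and the protocol nowhere describes post-baseline wear before a visit.

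Four stronger readings are tempting but unsupported:

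- *Week 39 has almost no usable data.* The wear is still collected, can be listed from source, and can enter the EOT value when dosing continues long enough.
- *The window always ends before the visit.* Visits on Day 267 to 273 are allowed and fall inside it, though all but the one edge case still yield too few days.
- *The sleep endpoint fails in the same way.* SAP 5.5.5 names no derived sleep variable and defines a complete day only for DLPA, so the window calculation does not establish this.
- *Early stopping is mishandled.* Only listing data after EOT keeps off-treatment wear out of on-treatment values and is not a defect.

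**Conclusion.** The mismatch is real and minor. If wear follows site visits, as the protocol says, and the DLPA variables are derived, the Week 39 row is missing for 15 of 15 allowed visit days with next-day wear and for 14 of 15 with same-day wear. These are counts of visit days, not forecasts of participants. On-time Week 12, 20 and 26 wear is split 6/8 or 7/7, so values can carry the labels Week 15, 23 or 29.

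The EOT value does not repair this. It is anchored to last dose and may hold Week 26 wear or wear from after Week 39, so it should not be read as a Week 39 value.

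The result rests on 14 days of wear beginning on the visit day or the day after. The primary endpoint is not touched, and no test or summary in SAP 3.0 depends on these windows.

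**What to change.** Reconcile protocol 8.2.2.3.2 with SAP Table 5, stating when post-baseline wear starts relative to the visit.

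If wear follows visits, replace the post-baseline blocks in Table 5 with 14-day windows that start after each participant's actual site visit, up to and including Week 39. Keep the 7-complete-day rule, restrict to days on study intervention, and label each value by the visit it follows. The planned wear then lies inside its own window: 14 days with next-day start, 13 with same-day start if the window opens the day after the visit. Even a fixed Day 275 to 288 window would be valid for 15 of 15 visit days with next-day start and 14 of 15 with same-day start, but windows tied to the actual visit avoid that dependence.

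The cost is an edit to the SAP table and to the window derivation, with no new data. There are two small downsides: the Week 39 value then covers about Weeks 39 to 41, and any wear between visits is listed only. The EOT row may stay, labelled as EOT and not used in place of Week 39. If only source data are listed, a note giving the wear dates relative to the visit is enough.

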5.5.6. Time to all-cause death up to EOMOP

Deaths will be listed only using the Randomized Set (RS).

5.5.7. Rate of all-cause death or unplanned PH-related hospitalizations up to EOMOP

Unplanned PH-related hospitalizations will be listed only using the Randomized Set (RS).

5.5.8. Change from baseline up to Week 39 in SF-12 scores

SF-12 individual questions responses will be listed only using the Randomized Set (RS). If available for analysis, the physical and mental component summary scores will be reported according to the instrument's instruction (and applying the OPTUM process).

5.5.9. Change from baseline up to Week 39 in the KSQ scores

KSQ individual questions responses will be listed only using the Randomized Set (RS).

5.5.10. Change from baseline up to Week 39 in the PAH-SYMPACT scores

PAH-SYMPACT individual questions responses will be listed only using the Randomized Set (RS).

5.5.11. Change from baseline up to Week 39 in the PGA-S scores

PGA-S individual questions responses will be listed only using the Randomized Set (RS).

5.5.12. Change from baseline up to Week 39 in the CGI-S scores

CGI-S individual questions responses will be listed only using the Randomized Set (RS).

5.5.13. Change from baseline up to Week 39 in the CGI-C scores

CGI-C individual questions responses will be listed only using the Randomized Set (RS).

5.5.14. Change from baseline up to Week 39 in NT-proBNP serum levels

NT-proBNP values will be listed only using the Randomized Set (RS).

5.5.15. Change from baseline up to Week 39 in other hemodynamic variables (including cardiac output [CO], CIn, mean right atrial pressure [mRAP])

Other hemodynamic variables (including cardiac output [CO], CIn, mean right atrial pressure [mRAP]) will be listed only using the Randomized Set (RS).

5.5.16. Change from baseline up to Week 39 in the number of low-risk criteria

This endpoint is derived based on other endpoints and will not be computed for this study, due to the very limited number of study participants.

5.6. Safety Analyses

All safety analyses will be based on the safety analysis set based on actual intervention received, unless otherwise specified. Analyses will be conducted for the entire study period only.

For all continuous safety variables, descriptive statistics by intervention group will include the N, mean, standard deviation, median, minimum, and maximum. Categorical variables will be summarized by intervention group using frequency counts and percentages.

5.6.1. Extent of Exposure

Exposure will be summarized for the entire study period, by treatment group and overall using the SAS.

The number and percentage of participants who receive study intervention will be summarized. The number and percentage of participants at each dose level will also be summarized by visit.

Descriptive statistics for duration of study intervention (N, mean, SD, median, and range (minimum, maximum)) will be summarized. Participant-[years] of intervention are calculated as [days of intervention/365.25]. Participant-[years] will be presented by intervention group.

Cumulative exposure will be summarized using week categories.

Study intervention duration is defined as (date of last dose of study intervention – date of first dose of study intervention) +1.

Total dose days of intervention is defined as the total number of days that study intervention was administered to the participant (excluding days off study intervention).

The number (%) of participants with a dose adjustment/dose not administered will be summarized by intervention group. Reasons for dose adjustments/doses not administered will also be summarized.

Descriptive statistics will be presented for the following parameters: Maximum Study Treatment Total Daily Dose and Weighted-Average Study Treatment Total Daily Dose (separately for titration and maintenance periods); Individual Total Daily Maintenance Dose of Study Treatment; Maximum Tolerated Total Daily Dose of Study.

The mean daily dose of study treatment is calculated as (sum of total daily dose)/study treatment duration.

5.6.2. Adverse Events

The verbatim terms used in the CRF by investigators to identify adverse events will be coded using the Medical Dictionary for Regulatory Activities (MedDRA). Any AE occurring at or after the initial administration of study intervention through the day of last dose plus 3 days is considered to be treatment emergent. If the event occurs on the day of the initial administration of study intervention, and either event time or time of administration are missing, then the event will be

assumed to be treatment emergent. If the event date is recorded as partial or completely missing, then the event will be considered to be treatment emergent unless it is known to be prior to the first administration of study intervention based on partial onset date or resolution date. All reported treatment-emergent adverse events will be included in the analysis. For each adverse event, the number and percentage of participants who experience at least 1 occurrence of the given event will be summarized by intervention group.

Summaries will be displayed by treatment (selexipag or placebo) and will include all events up to 3 days after the last dose of study drug or EOS, whichever occurs first.

Summary tables will be provided for treatment-emergent adverse events:

- AEs
- Serious AEs (SAEs)
- AEs leading to discontinuation of study intervention
- AEs by severity
- AEs by relationship to study intervention
- All SAEs up to 30 days after the last study treatment

In addition to the summary tables, listings will be provided for participants who:

- Had AEs
- Had SAEs
- Had AEs leading to discontinuation of study intervention
- Had AEs of COVID-19
- AEs of special interest ([Appendix 8](#))

Deaths will be displayed by actual intervention received. Frequencies for the following parameters will be included in the summary table:

- Number of participants who died
- Cause of death
- Relationship to study intervention (yes/no)

A listing of participants who died will be provided.

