### 7.1.1. Temporary Discontinuation

Study intervention may be temporarily interrupted in response to an AE, a diagnostic or therapeutic procedure, a laboratory abnormality, or for administrative reasons.

Interruptions of study intervention must be kept as short as possible. Any study intervention interruption of 3 days or more will require a new up-titration starting with 1 tablet of study intervention (200 µg) twice daily/once daily. For each participant, the up-titration frequency will be up to the medical judgment of the investigator and based on his/her clinical evaluation of the participants' tolerability of the study drug prior to its interruption (see Section 6.1.2). Re-uptitration to a previously reached dose can be done at scheduled or unscheduled TCs or visits, respectively.

Study intervention interruptions exceeding 14 consecutive days must lead to permanent discontinuation of study intervention (see Section 7.1).

Interruptions of 1 day or more must be recorded in the eCRF.

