
 To assess the overall safety of selexipag 	
 Intervention-emergent AEs. Intervention-emergent prostacyclin-associated AEs. Serious adverse events (SAEs) up to End-of-Study (EOS). AEs leading to premature discontinuation of study intervention. Intervention-emergent AEs of special interest (eg, hypotension, anemia, hyperthyroidism). Change in vital signs (systolic and diastolic arterial blood pressure and pulse rate) and body weight from baseline to all assessed timepoints during the study.

Objectives	Endpoints
	
 • Intervention-emergent marked laboratory abnormalities. • Change from baseline in supplemental oxygen rate. • Change from baseline in forced vital capacity (FVC) and diffusing capacity of the lung for carbon monoxide (DLCO). • Change from baseline in arterial blood gas parameters.

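### The summary table of AEs leading to discontinuation is limited to onset within 3 days of last dose, so it can omit a late-onset AE during an interruption that then ends treatment

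*SAP*

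**What the plan says.** SAP 5.6.2 defines the window: an AE at or after the first administration "through the day of last dose plus 3 days is considered to be treatment emergent". The same section applies this to the by-arm summaries, which "will include all events up to 3 days after the last dose of study drug or EOS, whichever occurs first". It then states "Summary tables will be provided for treatment-emergent adverse events" and lists AEs leading to discontinuation of study intervention among them.

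Some outputs in 5.6.2 reach further. One table covers "All SAEs up to 30 days after the last study treatment", and there is a separate deaths table. "In addition to the summary tables, listings will be provided for participants who" had AEs, SAEs or AEs leading to discontinuation, and no 3-day limit is stated for these listings.

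The endpoint behind the table, in SAP 1.1 and protocol Section 3, is "AEs leading to premature discontinuation of study intervention". Neighbouring endpoints (AEs overall, prostacyclin-associated AEs, AEs of special interest, marked laboratory abnormalities) are qualified as intervention-emergent. This one is not.

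Protocol 9.5.2 says the AE summaries take in every event collected during the study. Protocol 8.4.1 collects AEs from consent to the end-of-study visit or last contact.

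Protocol 7.1.1 allows temporary interruption for an AE, a procedure, a laboratory abnormality or administrative reasons. It sets the limit: "Study intervention interruptions exceeding 14 consecutive days must lead to permanent discontinuation of study intervention". Neither document says how to classify an AE that starts during an interruption.

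**The concern.** When an interruption turns into permanent discontinuation, the last dose is the intake before the gap. A new AE that begins on, say, off-drug day 5 and prevents a restart then lies beyond last dose plus 3 days. It is not treatment-emergent, so it is left out of the summary of AEs leading to discontinuation, although it is an AE that led to discontinuation.

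The by-arm count for a stated safety endpoint could therefore be too low. The disposition summary in SAP 5.2 tabulates reasons for stopping study intervention by group with no such window, so the two tables could disagree about the same participant with no stated explanation. Under SAP Section 2 no hypothesis is tested and efficacy is only listed, so the safety summaries are the main by-arm comparison left in the report.

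**Working it through.** The plan states no figure on this point, so there is nothing to reproduce. The check applies the 5.6.2 rule to each possible onset day.

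**Inputs**
- Window tail: 3 days after last dose (SAP 5.6.2).
- Longest interruption that still permits a restart: 14 consecutive days (protocol 7.1.1).
- Tail of the SAE table: 30 days after last treatment (SAP 5.6.2).

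**Step 1: classification by onset day.** Call the last dose before the gap day 0 and let the AE start on off-drug day k. If dosing never resumes, the AE is treatment-emergent only if k ≤ 3. If dosing resumes, the last dose falls after onset, so the AE is treatment-emergent for every k.

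| Onset day k | Dosing resumes | Dosing does not resume |
|---|---|---|
| 1 to 3 | counted | counted |
| 4 to 14 | counted | not counted |

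The omission therefore needs k ≥ 4.

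**Step 2: range of onset days exposed.** For a gap of g days, the number of onset days outside the window without a restart is max(0, g − 3).

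| Gap g (days) | Onset days outside the window |
|---|---|
| 3 | 0 of 3 |
| 4 | 1 of 4 |
| 7 | 4 of 7 |
| 10 | 7 of 10 |
| 14 | 11 of 14 |

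These are counts of calendar days, not of events.

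**Step 3: where a late-onset AE that ends treatment would still be reported.** Take k = 5 with no restart.
- *Non-serious:* 5 > 3, so it is in none of the treatment-emergent tables. It is in the listings.
- *Serious:* 5 ≤ 30, so it is in the 30-day SAE table and the listings. With a 30-day tail, 0 of the 14 onset days are lost. That table is not described as showing which SAEs ended treatment.
- *Fatal:* also in the deaths table.

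**Step 4: text against text.** The endpoint has no intervention-emergent qualifier, but the table that reports it does. Protocol 9.5.2 puts all collected events in the AE summaries, while SAP 5.6.2 stops them at last dose plus 3 days. SAP Appendix 2, which is headed as the changes to protocol-planned analyses, describes the simplified reporting after termination and does not mention this cut-off.

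**The case against.** The strongest reply is that the sequence is unusual. Where dosing is interrupted because of an AE, that AE normally began on drug and is inside the window. The same holds for an AE on drug that leads straight to stopping. The omission needs a separate AE, starting at least 4 days after the last dose, that becomes the reason treatment ends. The study was terminated for slow enrollment, SAP 5.5.16 refers to a very limited number of participants, and the AE analyses are descriptive, so a reader of the participant-level listing could find such a case. All of this stands, and it limits the importance of the point. It does not change the fact that the listing gives no by-arm count and that, for a non-serious AE, no AE summary table recovers the event.

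A second reply is that removing the limit from one table leaves the remaining treatment-emergent tables dependent on whether dosing resumes, and lets an AE appear in the discontinuation table but not in the all-AE table. That is correct, and it is why the fix includes a footnote.

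A reader might infer more than the documents support:
- *That any AE starting during an interruption is dropped if it ends treatment.* Onset on off-drug days 1 to 3 is counted either way, and the loss is from the treatment-emergent summary tables, not from all reporting.
- *That 11 of 14 is the share of such AEs lost.* It is a share of onset days in a full 14-day gap, and it could stand for a share of events only if onset were spread evenly over gaps of that length. Nothing in the documents supports that assumption.
- *That the loss is larger in one arm.* No interruption rates are given for either arm.

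**Conclusion.** The point holds in a narrow form. As written, SAP 5.6.2 can leave out of the by-arm table of AEs leading to discontinuation an event that the endpoint is meant to count. The cut-off is also narrower than protocol 9.5.2, and Appendix 2 does not record the difference.

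The number of events affected is unknown, because neither document gives rates of interruption or of AEs during interruption. It may be zero in this study. What is exposed is mainly non-serious AEs with onset more than 3 days after last dose that then cause permanent discontinuation.

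The conclusion assumes that last dose means the last intake actually taken, which the SAP does not define further, and that the listings carry no 3-day limit, since none is stated. It is worth acting on because the correction is small and brings the table into line with its endpoint, not because a material distortion has been shown.

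**What to change.** Three edits to the SAP:

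1. In 5.6.2, base the summary of AEs leading to discontinuation on all AEs with onset on or after first dose whose action taken is permanent discontinuation of study intervention, with no limit at last dose plus 3 days.
2. Footnote any event in that table with onset more than 3 days after last dose, because it will not appear in the table of all treatment-emergent AEs.
3. In Appendix 2, record that the 3-day cut-off kept for the remaining AE summaries departs from protocol 9.5.2.

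The cost is a few lines of text and one changed filter. It should need no new data, assuming the field that identifies these AEs for the planned table and listing is already collected. The downside is that a few events with onset off drug may enter this table, which the footnote makes visible. The other treatment-emergent tables still depend on whether dosing resumes; the Appendix 2 entry discloses their cut-off but does not remove that dependence.
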